The progress of the study will be monitored by the Data Safety Monitoring Board (DSMB) on a semi-annual basis. The DSMB chair is [name], and additional members include [name] and [name]. On a semi-annual basis, the Project Leaders (Drs. [name], [name], [name], [name], and [name]), the Project Manager, and Project Analyst will prepare a written report on the progress of the study including data on enrollments, comparison

of target to actual enrollment, overall status of the study patients, information on race/ethnicity and sex, and information on any serious adverse events. Following review of these reports, the DSMB will recommend any modifications that are required to enhance recruitment and retention of study patients. Participating hospitals each have designated safety officers as well, who will help ensure the safety of participants. This protocol presents minimal risks to participants and interim analyses of trial outcomes are not considered crucial for the protection of human subjects.

- Overview of the DSMB

The purpose of the DSMB is to provide the oversight and monitoring necessary to ensure the safety of the study participants and the validity and integrity of the trial data. The study governance provided by the DSMB is distinct from the review and approval by an Institutional Review Board (IRB) or any independent adjudication committee. The members of the DSMB have relevant expertise in the operational, medical, and biostatistical aspects of a clinical trial. The DSMB will advise the principal investigator (PI) and the study sponsor (NHLBI) regarding the continuing safety of study participants, the ongoing validity and scientific merit of the trial and whether or not the study should continue.

- DSMB Membership and Chair

The ability of the DSMB to provide additional assurance of participant safety and scientific validity depends on the appropriate selection of its Board members. The DSMB will be composed of Board members with expertise in pediatrics, pediatric respiratory illnesses, pediatric hospital care, quality and safety, and clinical trials. The DSMB will have a designated Chair. The role of the DSMB Chair is to provide leadership on administrative and scientific issues. The chair will: facilitate discussions on trial related topics; integrate differing points of view from the Board members; and establish a consensus on recommendations to the study sponsor.

Any concerns noted will be brought to the attention of the DSMB Chair who will take appropriate action. The DSMB will review on a semi-annual basis the reports prepared by the study PI, statistician, and programmer/analyst on the progress of the project, including: data on enrollments; comparison of target to actual enrollment; overall status of the study participants; information on race/ethnicity; gender; and serious adverse events. The DSMB will also determine whether additional effort is required to foster the progress of the study, and whether serious adverse events were immediately reported to the UCSF Committee on Human Research and dealt with appropriately. The DSMB will determine whether the study should continue, be terminated, or be modified based on observed beneficial or adverse effects.

- DSMB Responsibilities

Prior to implementation of the trial, the DSMB will evaluate the study design, review informed consent documents and plans for recruitment, adherence, interventions, data quality and safety monitoring. At periodic intervals during the course of the trial, the responsibilities of the DSMB are to:

- Evaluate the progress of the study, including, adequacy and timeliness of participant recruitment, adherence to the interventions protocol, data quality and timeliness, participant safety, and other factors that can affect study outcome;
- Consider factors external to the study when relevant information, such as scientific developments, may have an impact on the safety of the participants or the ethical conduct of the trial;
- Ensure data integrity;
- Ensure confidentiality of data and the results of monitoring;

• Report to the study sponsor and investigators on the scientific progress of the trial and the safety of participants;

• Make recommendations to the study sponsors and Investigators and Institutional Review Boards on continuation, termination, or other modifications of the trial.

- DSBM Process

The DSMB will meet semi-annually by videoconference. Agendas for the meetings will be developed by the PI and the DSMB Chair. The first meeting should take place before initiation of the study to discuss protocol, interventions, safety measures and to establish guidelines for monitoring. Following the initial meeting, the DSMB should meet semi-annually. An emergency meeting of the DSMB may be called at any time by the Chair or study sponsor should questions of participant safety arise.

DSMB meetings will consist of an open and a closed session. The open session may be attended by investigators and study sponsor staff, and they should always include the principal investigator and the study biostatistician. Issues discussed at the open session will include conduct and progress of the study, recruitment, adherence with the visit and interventions protocols, data quality and timeliness, problems encountered and aggregate outcome data. The closed session will be attended only by DSMB members and appropriate study sponsor staff representative(s), but others may attend if requested by the DSMB. All discussion at the closed session is completely confidential.

Should the DSMB decide to issue a recommendation to terminate or alter the study protocol, a full vote of the DSMB will be required. In the event of a split vote, a simple majority vote will rule and a minority report should be appended. The DSMB will review the protocol of approved and funded studies ancillary to the study, but they will not review the conduct and outcomes of these studies.

- DSMB Recommendations

The DSMB Chair will prepare minutes of the open and closed sessions, including any recommendations for changes in the study protocol that are approved by the Board and sent to study sponsor. The study sponsor Project Scientist will distribute minutes of the open session to the Principal Investigators within four weeks of each meeting. The minutes of each DSMB closed session should conclude with a recommendation to continue, terminate or alter the study. A recommendation to terminate the study or alter the study protocol may be made by the DSMB at any time by majority vote. Such recommendations will be transmitted to the study sponsor. Recommendations of the DSMB that are accepted by the study sponsor will be transmitted by the Project Scientist to the Principal Investigator as rapidly as possible. In the event of a split vote in favor of continuation, a minority report should be included in the regular DSMB closed report.

Plans for Assuring Compliance with Requirements Regarding the Reporting of Serious Adverse Events

This trial intervention consists of clinical pathways that remind clinicians of current standards of care. It does not involve experimental treatments or diagnostic tests. Given the nature of this intervention, serious adverse events (SAEs) have been defined and will be monitored as follows. SAEs are defined as: 1) events that lead to patient harm/morbidity (reported via hospital safety/incident reporting systems), or 2) death/mortality. Local Project Leaders at participating hospitals will be notified to contact the UCSF Core Study Team immediately should SAEs occur, and they will also be contacted monthly throughout the trial period via survey to inquire about any SAEs. If any SAEs are reported, the PI and Project Manager are responsible for reporting to

the Core Investigator Team, DSMB, and the UCSF Human Subjects Committee within 48 hours. The Core Investigator Team, DSMB, local Project Leader, and Local Safety Officers will then use root cause analysis (RCA) methods to review any events to determine attribution to the SIP intervention. A central tenet of RCA is to identify underlying problems that increase the likelihood of errors while avoiding the trap of focusing on mistakes by individuals. RCA thus uses the systems approach to identify both active errors (errors occurring at the point of interface between humans and a complex system) and latent errors (the hidden problems within health care systems that contribute to serious adverse events).

G Statistical Plan

G1 Sample Size Determination and Power

For sample size calculations, we used an alpha of 0.05, effect size estimates based on prior literature (see Table), and intra-class correlation coefficients (ICCs) specific to each outcome. ICCs were calculated based on our baseline period data (12-month period prior to trial intervention). We identified 40 hospital sites, and we accounted for up to 20% drop out of hospitals over the course of the trial (n=32 hospitals). We found that with volumes of 10 children with asthma, 15 children with pneumonia, and 15 children with bronchiolitis per year per hospital, we have >80% power to detect previously reported effect sizes in mean adherence to these evidence-based practice measures. If 32 hospitals (80%) remain from the 40 hospitals we have enrolled, we will have estimated minimal sample size of 3,840 admissions in the study (32 hospitals X 40 admissions per year X 3 years [1-year baseline and 2-year intervention period]).

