Design: A parallel, cluster-randomized trial best addresses seasonal variation in outcomes for these respiratory illnesses by providing a concurrent control group and collecting data over 5 respiratory viral seasons, 3 seasons prior to implementation and 2 seasons after implementation. We will stratify hospital randomization by geographic region (e.g., Northeast) to help ensure the effects of seasonal variation are similar across intervention and control groups. Figure 3 shows the study timeline. In Year 1, we will recruit and randomize hospitals to intervention versus wait-list control, and chart reviewers will collect baseline data (before implementation). In Year 2, we will begin implementation in the intervention hospitals. Hospitals in the wait-list control arm will wait/not implement pathways until Year 4.

E2 Subject Selection

2.a Inclusion and Exclusion Criteria

The study sample will include children admitted to the inpatient pediatric wards of study hospitals for asthma, pneumonia. or bronchiolitis during the study period. We will identify eligible children using ICD-10 codes that were developed and validated as part of the NHLBI-funded PRIMES Studies (Pediatric Respiratory Illness Inpatient Measurement System, R01HL121067 and R01HL088503).48,51 For asthma, codes include J4520, J4521, J4522, J4530, J4531, J4532, J4540, J4541, J4542, J4550, J4551, J4552, J45901, J45902,

Table 3. Study Inclusion/Exclusion Criteria

Inclusion Criteria:

Primary diagnosis of asthma AND age >2 to <18 years-old at time of admission to the hospital

Primary diagnosis of pneumonia AND age >2 months and <18 years at time of admission to the hospital

Primary diagnosis of bronchiolitis AND age <2 years at time of admission to the hospital

Exclusion Criteria and Rationale:

Secondary diagnosis of SARS-CoV-2 (due to lack of evidence-based guidelines on management)

Transfer in from or out to an inpatient facility (due to inability to accurately determine length of hospital stay)

Pre-existing chronic lung disease (other than asthma), cardiovascular disease, airway anomalies, immunodeficiency, or neurologic disorders*

*The pathway intervention excludes these children because it is intended for routine management of the targeted respiratory conditions, not for children who are critically ill or have underlying chronic illness

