proportion of eligible patients with pathway-based order sets accessed (process measure) and guideline adoption outcomes (Table 1). Reports will contain hospital-specific performance and aggregate performance across all intervention sites. Local implementation teams will hold monthly meetings with all clinicians and staff involved in the care of children with respiratory illnesses. In the meetings, they will use these reports to review local performance.

- PDSA cycles: Local implementation teams will review clinical workflows in relation to current performance and plan PDSA cycles, in which teams identify and test workflow changes to improve performance.⁵² PDSA cycles facilitate progressive, structured, and iterative change.
- Integration of pathway content into electronic order sets: In order to promote sustainability, local implementation teams will integrate guidance on evidence-based practices into electronic order sets. The Core Investigator Team will provide these teams order set templates to guide this process and mentors will support site leaders in planning and addressing barriers.
- Mentor meetings/facilitation: Monthly meetings of the mentors and implementation teams will involve: 1) reviewing performance reports on adoption of evidence-based practices, 2) developing project plans with key milestones/targets and monitoring progress, and 3) planning PDSA cycles.
- Learning Collaborative: Monthly mentor calls will periodically involve implementation leaders from all 2-3 sites the mentor is assisting. These group calls will facilitate cross-site problem solving and sharing of insights on barriers and facilitators of implementing the multi-condition pathway intervention.

3.b Method for Assigning Subjects to Intervention Groups

We will cluster-randomize participating hospitals to 2 different intervention start dates as described above in "E1 Overview and Study Design." All children hospitalized after a hospital's intervention start date will be considered "exposed" to the intervention.

3.c Fidelity Monitoring

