During the first 12 months of intervention implementation, we will collect data via monthly electronic survey of local implementation leaders. Surveys will measure utilization (yes/no) of implementation strategies²⁵ in the prior month. Each month, mentors will verbally verify these yes/no survey responses (during scheduled mentor meetings). In addition, during scheduled field visits to sites in month 4 after start of the intervention period, mentors will visually verify the integration of pathways into electronic order sets. Surveys will inquire about prior or concomitant interventions to improve pediatric respiratory illness care quality. Surveys will also collect quantitative estimates of the monthly time costs of implementation for local implementation leaders; and qualitative, free-text responses on any unintended negative consequences of implementation.

3.d Prior and Concomitant Interventions

See above section "E3 3.c Fidelity Monitoring."

F Study Procedures

F1 Screening for Eligibility

See above section "E2 2.a Inclusion and Exclusion Criteria."

F2 Data Collection/Study Outcome Measurement

Chart reviewers at each hospital will collect data through monthly chart review of the electronic health records of enrolled patients. All hospitals (both intervention and wait-list control) will collect baseline data in Year 1 and then continue data collection in Years 2-3, while intervention hospitals implement pathways and control hospitals continue to wait. Only wait-list control hospitals will collect data in Year 4, when they implement the intervention. We will collect data on the outcomes described in Table 1 as well as several patient characteristics known to be associated with the severity of these respiratory illnesses in children (see below in "Primary Analysis").

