[name] and the UCSF Project Manager will train chart reviewers at each study site based on the Medical Record Abstraction Quality Assurance and Control Framework.⁵³ Principles of the framework include: 1) quality assurance– prospective actions taken such as abstractor training, standard procedures, and job aids to assure adequate accuracy, and 2) quality control—measurement of error or discrepancy rates and use of the measurements to guide adjustments to controllable inputs to the abstraction process, such as abstraction tools, procedures, and training. A second chart reviewer will review a subset of charts (10%) each month at each site for quality control, providing feedback to the primary reviewer, [name], and the UCSF Project Manager about any discrepancies (to facilitate additional training).

Reviewers will enter data into the REDCap electronic database, accessible from all study sites. To maximize data quality, we will use REDCap data validation algorithms, which restrict input to plausible values and check for potentially erroneous outliers. The UCSF Project Manager will check for suspicious or missing data weekly and contact chart reviewers to make any needed corrections. We will store all data securely (see Protection of Human Subjects, Facilities). Our team has extensive experience using these methods of chart reviewer training and quality control/assurance in community hospitals. 9,54 For any issues with REDCap, our central study team should be contacted ([contact]).

SHM will create a project website in which all project materials will be stored in the WorkZone platform. All site leaders and chart reviewers will be provided individual usernames and passwords to access this website at anytime throughout the study. The SHM team can be contacted to help with access ([contact]). Project materials will include chart review training and reference materials (including site-specific REDCap data entry links), the multi-condition pathway implementation toolkit, performance reports, mentor/facilitator meeting notes, educational videos, and project timeline.

F3 Safety Monitoring and Serious Adverse Event Reporting

The Data and Safety Monitoring Plan for this grant application incorporates the Policies on Data and Safety Monitoring specified by the Department of Pediatrics at the University of California, San Francisco.

Monitoring the Progress of the Study

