For our primary outcome, we will perform exploratory subgroup analyses to understand effects by different subgroups: 1) hospital type [community hospital, nested children's hospital], and 2) additional demographic characteristics [race, ethnicity, primary language, and primary insurance]. We will conduct these analyses to quantify and understand effects sizes across these important subgroups. We will also test interaction terms to see if any differences in effect sizes by subgroup are significant.

Sensitivity Analyses:

In our primary analysis, we will adjust for patient age, sex, need for supplemental oxygen, and prior prescription of inhaled corticosteroid (applies only to admissions for asthma). In a sensitivity analysis, we will incorporate additional demographic factors including race, ethnicity, primary language, and primary insurance [proxy for socioeconomic status]. This will be done to make sure our effects are robust even if these covariates were imbalanced by randomization. Additionally, we will examine an "all-or-nothing" outcome across all conditions (asthma, pneumonia, and bronchiolitis), where we analyze if all 2-3 evidence-based practices that apply for a given admission were adhered to or not. Although our difference-in-differences approach should account for differential adherence to evidence-based practices before the intervention, if we find significant discrepancy in baseline adherence in control versus intervention hospitals such that we would be concerned about floor/ceiling effects (limited ability to improve), we will perform an additional sensitivity analysis in which we formally incorporate mean adherence to evidence-based practices at baseline/before the intervention at the hospital level into our models. Lastly, we have also collected prospective data on intervention fidelity and interventions that could lead to potential contamination in the control arm. If we find low fidelity in the intervention arm or potential contamination in control arm hospitals, we will also incorporate these data into a sensitivity analysis.

Fidelity/Aim 2 Analysis:

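### As written, the project website opens intervention materials to wait-list hospitals before their Year 4 start, an avoidable contamination risk

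*Combined protocol and SAP*

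**What the plan says.** F2 (Data Collection/Study Outcome Measurement) sets up a single site: "SHM will create a project website in which all project materials will be stored in the WorkZone platform". It then grants access: "All site leaders and chart reviewers will be provided individual usernames and passwords to access this website at anytime throughout the study". Besides chart-review training, reference materials and site-specific REDCap links, the listed contents are "the multi-condition pathway implementation toolkit, performance reports, mentor/facilitator meeting notes, educational videos, and project timeline".

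F2 also shows that the wait-list arm has working chart reviewers during the comparison: "All hospitals (both intervention and wait-list control) will collect baseline data in Year 1 and then continue data collection in Years 2-3".

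E1 (Overview and Study Design) sets the timing of the two arms: "In Year 2, we will begin implementation in the intervention hospitals", and "Hospitals in the wait-list control arm will wait/not implement pathways until Year 4".

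E3 3.a describes the performance reports: "Reports will contain hospital-specific performance and aggregate performance across all intervention sites".

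On contamination, the Sensitivity Analyses part of G2 says that relevant data have been collected prospectively and promises a conditional extra analysis. The sentence, short of its last word, reads: "If we find low fidelity in the intervention arm or potential contamination in control arm hospitals, we will also incorporate these data into a sensitivity".

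**The concern.** The primary analysis in G2 compares the change in mean adherence from baseline between the two arms. The wait-list hospitals are the only concurrent control, so the comparison depends on their practice staying free of the intervention through Years 2-3.

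F2 works against this. It places what control sites need (abstraction training, data-entry links) beside what they should not yet have (toolkit, videos, mentor notes, reports) and gives one access rule for all of it. Section A describes pathways as simple visual diagrams, usable on paper, so the stored material is itself part of the intervention. The site leaders are physicians with quality-improvement expertise (J1), and those surveyed rated the intervention as feasible and acceptable (B1). In E2 2.b, the protocol argues against seeking consent partly because disclosing the study's purpose could change staff behaviour. Open access to the toolkit at control sites sits badly with that argument.

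If control hospitals improved early because of these materials, the estimated effect would shrink, and a weak or null result would be harder to interpret.

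**Working it through.** **1. Does the access rule cover the wait-list arm?** F2 gives log-ins to every site leader and every chart reviewer. F2 also has wait-list hospitals reviewing charts in Years 1-3, and J1 describes local site leaders for the participating hospitals without distinguishing arms. The rule therefore covers both arms. In the list of contents, only the REDCap links are called site-specific. No section restricts content by arm or sets a release date.

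**2. How long is the exposure window?** Intervention start is Year 2 and wait-list start is Year 4: 4 − 2 = 2 years, which is the whole post-baseline comparison.

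**3. The plan's own figures (G1).** 40 hospitals × (1 − 0.20) = 32. Admissions per hospital per year: 10 + 15 + 15 = 40. Total: 32 × 40 × 3 = 3,840, which reproduces the stated minimum. The claim of more than 80% power cannot be reproduced, because neither the ICCs nor a standard deviation is given.

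**4. Effect size for scale.** The seven increases in Table 1 are 30, 27, 20, 25, 8, 13 and 9 points. Their sum is 132, and 132 / 7 = 18.9. Weighted by the G1 volumes, with condition means of 28.5 (pneumonia), 17.67 (asthma) and 11 (bronchiolitis): (15 × 28.5 + 10 × 17.67 + 15 × 11) / 40 = 19.2 points.

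**5. Dilution.** Let c be the share of the effect that reaches control hospitals. The documents give no value, so c is assumed. The contrast becomes 19.2 × (1 − c). For a design with exactly 80% power at two-sided 0.05 (G1 does not state sidedness), power = Φ(2.80 × (1 − c) − 1.96), where 2.80 = 1.96 + 0.84. The sample needed to restore power rises by 1 / (1 − c)².

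| c (assumed) | Contrast, points | Power if exactly 80% at c = 0 | Sample inflation |
|---|---|---|---|
| 0 | 19.2 | 80% | 1.00 |
| 10% | 17.3 | Φ(0.56) = 71% | 1.23 |
| 20% | 15.4 | Φ(0.28) = 61% | 1.56 |
| 30% | 13.5 | Φ(0.00) = 50% | 2.04 |

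**6. How far does this depend on the starting power?** I used a normal approximation with 16 hospitals per arm, and 40 baseline and 80 later admissions per hospital (ignoring the three-month exclusion in G2). The variance is V = (2/16) × [SD²(1 − ICC)(1/40 + 1/80) + 2 × SD² × ICC × (1 − CAC)], where CAC is the cluster autocorrelation, and power = Φ(0.192 × (1 − c)/√V − 1.96). Assumed ranges are SD 0.35-0.45, ICC 0.05-0.20 and CAC 0.5-1.0.

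- Least favourable corner (SD 0.45, ICC 0.20, CAC 0.5): V = 0.125 × (0.006075 + 0.0405) = 0.00582 and √V = 0.0763. Power is 71% at c = 0, 52% at c = 20% and 42% at c = 30%.
- Most favourable corner: power stays above 99% at all three values of c.

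The loss therefore ranges from negligible to about 30 percentage points, depending on inputs that the documents do not give.

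**The case against.** The strongest reply is that access is not uptake. The intervention is mentored implementation: audit and feedback, PDSA cycles, order-set integration, monthly mentoring and group calls (E3 3.a). The barriers that the protocol names for community hospitals are quality-improvement resources, EHR integration, consensus and staff training, and a log-in supplies none of these. F2 does not say when each item is uploaded, and individual accounts are compatible with folder permissions that the text does not describe. E3 3.a describes reports and mentor meetings in terms of implementation teams and intervention sites, so it is unclear how much of that content control users could reach. Any bias would be toward no effect and would not create a false positive.

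Most of this stands, and it limits the point in four ways.

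- A reader might infer that control hospitals effectively had the intervention two years early. The text supports access to materials, not use of them. Nor does it say that the website is the only route to REDCap.
- A reader might infer that the conditional sensitivity analysis is the only safeguard. It is not. Controls are told to wait (E1, F2), the DSMB reviews adherence to the intervention protocol (F3), and G2 reports prospective collection of contamination data.
- A reader might infer that a null result could never be told apart from contamination. That is too strong. The Appendix B chart form records asthma pathway orders, one of the seven practices, so a rise in the control arm would be visible for asthma, though its cause would not be.
- The power figures describe assumed values of c, not this trial.

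The reply does not remove the access rule itself. The instruction to wait restricts action, not access. The sensitivity analysis has no stated indicator or trigger. The only survey described as asking about other interventions covers the first 12 months of implementation (E3 3.c), so the documents do not show how control-site exposure is measured across Years 2-3.

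**Conclusion.** The point holds as a contamination risk written into the protocol. F2 gives wait-list staff log-ins to intervention materials throughout the study, E1 requires those hospitals to hold off until Year 4, and no section separates content by arm or date. The expected direction of any bias is toward no effect.

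Its size is unknown. The fall from 80% to about 71%, 61% or 50% rests on an assumed c of 10%, 20% or 30% and on starting power of exactly 80%. G1 claims more than 80%, and under favourable assumptions the loss is negligible. The documents do not show that contamination occurred. If folder permissions already differ by arm, the defect is only that the protocol does not say so.

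This should be fixed because the remedy is cheap and protects the only randomised contrast. It is not grounds for holding up or discounting the trial.

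**What to change.** **Protocol text.** In F2, replace the access sentence with an arm-specific rule. Until a hospital's own start date, its staff can open only chart-review training, chart-review reference materials and REDCap links. The toolkit, videos, mentor notes and performance reports are released at that start date, which is Year 4 for wait-list hospitals. If permissions already work this way, say so.

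**If access has already been open.** Version 1.6 is dated September 2025, and baseline data have already been used for the ICCs, so some or all of Years 2-3 may have passed. In that case, report that access was open. Before analysts are unblinded, define the contamination indicator for the G2 sensitivity analysis: website access records by hospital, if the platform keeps them, and the control-arm trend in asthma pathway orders. State what finding triggers the analysis, and that it conditions on post-randomisation exposure and so is not protected by randomisation.

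**Cost.** A permissions setting, one protocol sentence and a little extra analysis. Two limits remain. A late change cannot undo earlier exposure. Control reviewers will also still learn the target practices from the chart form itself, which permissions cannot prevent.
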